3.1 Efficacy Variables

3.1.1 Part 1

3.1.1.1 Primary Efficacy Endpoints

Not applicable.

3.1.1.2 Secondary Efficacy Endpoints

Not applicable.

3.1.1.3 Other Efficacy Endpoints

In Part 1, the following efficacy assessments will be collected in eCRF and will be summarized descriptively:

- International Standards for Neurological Classification of SCI (ISNCSCI) motor and sensory scores. The ISNCSCI scale includes a motor and sensory examination for each side of the body (left/right). Higher values indicate better function with the maximum scores corresponding to normal function. The following 4 subscores will be summarized:
 - Upper Extremity Motor Score (UEMS) with scores ranging from 0-50;
 - Lower Extremity Motor Score (LEMS) with scores ranging from 0-50;
 - Pin Prick Sensory Score with scores ranging from 0-112;
 - Light Touch Sensory Score with scores ranging from 0-112.
- Graded Redefined Assessment of Strength, Sensation and Prehension (GRASSP) scores (Kalsi-Ryan et al. 2012a, Kalsi-Ryan et al. 2012b). The GRASSP is a clinical impairment measure for the upper limbs through three domains

(strength, sensation and prehension) that are important in describing arm and hand function. Higher scores indicate better function.

The following 4 subscores will be summarized:

- Strength total scores (left and right) with scores ranging from 0-50 for each side;
- Sensation total scores (left and right) with scores ranging from 0-12 for each side;
- Prehension Ability total scores (left and right) with scores ranging from 0-12 for each side;
- Prehension Performance total scores (left and right) with scores ranging from 0-20 for each side.
- Spinal Cord Independence Measure (SCIM III) self-care and mobility domain scores (Catz et al. 2007, Itzkovich et al. 2007). The SCIM III is a questionnaire evaluating activities of daily living (ADL) regarding self-care, mobility, and respiration and sphincter management. Higher scores correspond to better ability to carry out ADL. The current study will employ the self-care and mobility subscores.

The following 2 subscores will be summarized:

- Self-care with scores ranging from 0-20;
- Mobility with scores ranging from 0-40.

The following efficacy assessments collected in eCRF will be listed:

- Additional items from the ISNCSCI: neurological level for sensory and motor for right and left, neurological level of injury, American Spinal Injury Association (ASIA) impairment scale, and zone of partial preservation for right and left;
- Data collected for the following additional measures: SF-36 Health Survey, Neuro-QOL Upper Extremity Function, International standards to document remaining autonomic function after spinal cord injury (ISAFSCI).

3.1.2 Part 2

The ICH E9 (R1) addendum on estimands and sensitivity analysis in clinical trials to the guideline on statistical principles for clinical trials came into effect on 30 July 2020. This section addresses the construction of estimands for the primary and secondary efficacy objectives. Each estimand is defined according to the following five attributes:

- The **treatment** condition of interest, and as appropriate, the alternative condition to which comparison will be made.
- The **population** of subjects targeted by the clinical question.

- The **variable** (or endpoint) to be obtained for each subject that is required to address the clinical question.
- The clinical question of interest in respect of **other intercurrent events** not covered through the precise specifications of treatment, population and variable.
- A **population-level summary** for the variable providing a basis for comparison between treatment conditions.

The primary efficacy and secondary efficacy endpoints were selected as the best available to provide assessments of changes in motor function, ability to carry out activities of daily living, and any important changes related to the patient's condition of chronic SCI. A brief description and rationale for each is as follows:

3.1.2.1 Estimand for the Primary Efficacy Endpoint: Bilateral Upper Extremity Motor Score (UEMS)

The primary estimand is the change from baseline in ISNCSCI Bilateral Upper Extremity Motor Score (UEMS) to Study Day 169 between AXER-204 and placebo in patients with chronic spinal cord injury (CSCI).

UEMS is the primary efficacy measure and represents the upper extremity component of the International Standards for Neurological Classification of Spinal Cord Injury (ISNCSCI) motor exam. Although historically a total motor score of 100 for all extremities was calculated, for the last decade it has not been recommended to add the upper limb and lower limb scores together. Examination of the metric properties of the motor score indicates that it should be separated into two scales, one composed of the 5 upper limb muscle functions on left and right, and one of the 5 lower limb muscle functions left and right, with a maximum score of 50 each (Marino and Graves 2004, Graves et al. 2006).

Based on the expected mechanism of action of AXER-204 and the focus on subjects with cervical cord injury, the upper limb score has been selected as the primary endpoint measure. The overall motor score remains part of the exploratory analyses. Similarly, other recent SCI therapeutic intervention clinical trials have included change in UEMS as the primary efficacy endpoint (Fehlings et al. 2018, Levi et al. 2019).

The ISNCSCI is the most well-established and validated scale of motor and sensory function in spinal cord injury treatment and rehabilitation. ISNCSCI assessments are standardized by the governing body American Spinal Injury Association in conjunction with the International Spinal Cord Society. The UEMS portion of the ISNCSCI evaluates muscle strength controlled by five myotomes on each side of

CONFIDENTIAL

the body. The muscles tested, the corresponding levels, and the expected functional relevance of each level are illustrated in Table 2.

Table 2	UEMS:	Neurological Levels ,	Muscles,	Functional	Importance for
Activities o	f Daily L	iving			

Spinal Level	Muscle	Personal Independence	Wheelchair Management	Transfers
	group	Independence	Management	
C5	Elbow	Type, feed	Manipulate brake,	
	flexors		push on the flat	
C6	Wrist	Drink, wash, shave,	Remove	From chair to
	extensors	dress upper body	armrests/	bed or car
			footplates	
C7	Elbow	Turn in bed, dress	Wheel over	From chair to
	extensors	lower body	uneven ground	toilet or chair
		,	5	or bath
C8	Finger	Bladder and bowel	Negotiate curbs	From chair to
	flexors	care	-	bath
T1	Small finger		Balance on rear	From chair to
	abductors		wheels	floor

Adapted from van Hedel and Curt (van Hedel and Curt 2006).

Scoring: Each muscle is given a score between 0 and 5 as follows (Rupp et al. 2021):

- 0 = Total paralysis
- 1 = Palpable or visible contraction
- 2 = Active movement, full range of motion (ROM) with gravity eliminated
- 3 = Active movement, full ROM against gravity
- 4 = Active movement, full ROM against moderate resistance in a muscle specific position
- 5 = (Normal) active movement, full ROM against full resistance in a musclespecific position expected from an otherwise unimpaired person

Figure 2 is provided to visually show the impact of each neurological level and the muscle groups impacted. The inclusion criteria for the trial selects a functionally homogenous group of patients in terms of impaired arm and hand function controlled by spinal cord nerves at the C5-T1 levels (UEMS =4-36, GRASSP PP = 4-17). Of note, this means that the trial enrolls subjects with cervical level injury with neurologically complete and incomplete injuries and spanning all ASIA impairment scale grades (A, B, C, D) for patients with SCI.

The minimum clinically important change for bilateral UEMS has been estimated to be 3-points for **acute and subacute** SCI patients with a mean time from injury of 52 days (Scivoletto et al. 2013). In general, cervical SCI patients with a clinically important change in UEMS also improved functionally. This correlation between change in UEMS and function may be anticipated given the muscle groups evaluated in the test and their utility for carrying out activities of daily living. UEMS typically remains stable for chronic SCI patients, it is anticipated that even small changes may be considered significant from the perspective of patients (Wu et al. 2015).

Thus, change in ISNCSCI UEMS provides a robust and well-established measure of muscle function with relevance to functional changes for patients.

3.1.2.1.1 Treatment Condition of Interest

The treatment condition of interest is AXER-204 administered every 21 days, and is compared against the alternative treatment condition of placebo administered every 21 days.

CONFIDENTIAL

3.1.2.1.2 Population

The population is subjects with chronic spinal cord injury (CSCI) defined through the inclusion and exclusion criteria as part of the clinical trial protocol version 4.0.

3.1.2.1.3 Endpoint

The endpoint is the change from baseline in ISNCSCI Bilateral Upper Extremity Motor Score (UEMS) to Study Day 169.

3.1.2.1.4 Handling of Intercurrent Events

The following intercurrent events are anticipated during the study. Table 3 describes how intercurrent events will be collected and handled within the analysis.

Table 3Handling of Intercurrent Events for the Primary Estimand

Intercurrent event	Data collection and analysis	
Important protocol deviation, including use of prohibited medication, prior to assessment scheduled on Study Day 169	Patients will be followed and data collected after the intercurrent event will be used in analysis in line with the treatment policy strategy, i.e. regardless of the intercurrent event.	
Did not receive at least 5 doses (~80%) of the planned cumulative number of doses of treatment		
Did not perform at least one post- baseline assessment	Patients who experienced the intercurrent event will be excluded from analysis in line with a principal stratum strategy.	
Discontinuation from the study prior to assessment scheduled on Study Day 169	Patient's measurements up until the time of the intercurrent event will be used in analysis in line with the while on treatment policy, i.e. the endpoint is only evaluable in patients who complete the assessment scheduled on Study Day 169.	

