## **15.6.** Analysis Populations

Safety Population: Safety outcomes will be assessed for all subjects who are given at least one dose of investigational product.

Full Analysis Set (FAS) Population: Efficacy outcomes will be evaluated using the FAS, defined as all subjects randomized, treated with at least 1 dose of investigational product, and with at least one post-baseline assessment of efficacy.

Per Protocol Population: The per protocol population will be a subset of FAS and include subjects who received at least 80% of study drug and have no major protocol deviations that would impact efficacy assessment.

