3.1.2.4.6 Sensitivity Estimands for the 3rd Secondary Efficacy Objective

The first sensitivity estimand is the same as section 3.1.2.1.6. Another sensitivity estimand will follow an alternative approach to intercurrent events (Table 5).

Table 5Handling of Intercurrent Events for the Sensitivity Estimand for
the 3rd Secondary Efficacy Objective

Intercurrent event	Data collection and analysis	
Important protocol deviation, including use of prohibited medication, prior to assessment scheduled on Study Day 169	Patients will be followed and data collected after the intercurrent event will be used in analysis in line with the treatment policy strategy, i.e. regardless of the intercurrent event.	
Did not receive at least 5 doses (~80%) of the planned cumulative number of doses of treatment		
Did not perform at least one post- baseline assessment	Patients who experienced the intercurrent event will be excluded from analysis in line with a principal stratum strategy.	
Discontinuation from the study prior to assessment scheduled on Study Day 169	Among patients who experienced the intercurrent event, the intercurrent event will be integrated in the response variable in line with the composite variable strategy, i.e. considered to be Non-Responder (4='No change').	

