6.4 Modified Intent to Treat Analysis set (Part 2)

The Modified Intent to Treat (mITT) Analysis Set consist of all Part 2 subjects who were randomized and had at least one dose of study treatment and at least one postbaseline ISNCSCI assessment. Efficacy outcomes for Part 2 will be evaluated using the mITT analysis set. Subjects will be analyzed according to their randomized treatment.

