6.7 Per Protocol Set (Part 2 only)

The Per Protocol Set (PPS) will be a subset of mITT and consist of subjects who received at least 5 doses (~80%) of the planned cumulative number of doses of study drug and have no important protocol deviations that might impact efficacy assessment.

The important protocol deviations leading to exclusion from the PPS may include but not limited to the following: violation of key inclusion/exclusion criteria, use of prohibited medications as defined by the study protocol or in discussion with the Sponsor and/or medical monitor, errors in treatment allocation, etc. All important protocol deviations leading to exclusion from the PPS will be reviewed and approved by the Sponsor prior to database lock and unblinding. Subjects will be analyzed according to their randomized treatment.

7. DATA Handling

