8.5.2.1.2 Sensitivity Analysis

Three sensitivity analyses will be performed for the primary efficacy endpoint.

• Multiple imputations assuming missing not at random (MNAR)

Sensitivity analysis will be performed using multiple imputations with unobserved data imputed prior to fitting the linear regression. An assumption of MNAR will be made based upon an approach using multiple imputations with missing data for all subjects imputed from a regression model estimated from patients in the placebo group who stay on until Study Day 169. The imputation model will include the randomization strata and the corresponding baseline value as predictor. The method of multiple imputations (MI) (Ratitch et al. 2013) using Pattern Mixture Model (Little and Wang 1996) will be used. The amount of non-monotone missing data is expected to be minimal and hence any non-monotone missing bilateral UEMS will be imputed using the Markov Chain Monte-Carlo method. SAS PROC MI

and MIANALYZE will be used to generate 100 complete datasets and combine the results from each complete dataset analyzed using the same MMRM model as described above in section 8.5.2.1.

• Multiple imputations assuming missing at random (MAR)

An assumption of Missing at Random (MAR) will be made and subject's missing bilateral UEMS data will be imputed using those with available data within the treatment group they were assigned to using an approach similar to above as described in section 8.5.2.1.

• Excluding patients with important protocol deviations and who did not receive 80% of the planned treatment

An analysis excluding patients with deviations that may affect the efficacy of the study treatment will be conducted in per protocol set. The same MMRM method as the primary analysis as described in section 8.5.2.1 will be used. This analysis will use the principal stratum strategy, to assess the sensitivity of the results to the occurrence of the intercurrent events like important protocol deviations prior to assessment scheduled on Study Day 169 and not receiving at least 5 doses (~80%) of the planned cumulative number of doses of treatment as described in section 3.1.2.1.6.

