9.3 Analysis population

PK Analysis set and ADA analysis set were added in the SAP for analysis for PK and ADA, respectively. In addition, mITT analysis set was added for Part 2 and all Part 2 efficacy analysis will be conducted using mITT analysis set.

10. Changes in the Planned Statistical Analyses

The following changes in the planned statistical analyses indicated below are being made after all enrolled Part 2 patients have completed the 6-month visit, cleaning and unblinding of data, and completion of the 6-month top-line analysis for the primary, secondary and exploratory efficacy endpoints to compare treatment effects from baseline to Study Day 169 and prior to final database lock following 9-month visit or Study Day 253 (as described in section 2.2). The availability of results of this analysis was limited to the unblinded ReNetX staff and **Compare** Biostatistics and Programming team. The changes were requested by the unblinded ReNetX staff after review of results and approved by **Compare** Biostatistics and Programming team.

10.1 Post Hoc Exploratory Analysis for Efficacy Endpoints to Study Day 169

Results from the primary efficacy analysis, based upon a mixed-effects model for repeated measures (MMRM) as described in section 8.5.2.1, showed that there was no statistically significant difference at the two-sided 5% significance level between AXER-204 and Placebo groups in the primary efficacy endpoint. Additionally, the MMRM subgroup exploratory analyses (as described in section 8.5.2.1.3) did not show statistical significant difference between treatment and control groups in the primary endpoint at the unadjusted two-sided 5% significance level, but there is visually a potential trend toward treatment effect in the subgroups AIS grade (B, C, D) and no prior receipt of study drug in Part 1.

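### Dosed Part 2 subjects who leave with no post-baseline ISNCSCI fall outside every planned efficacy analysis, including the PGIC composite analysis and, by implication, the placebo-based MNAR imputation

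*SAP*

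**What the plan says.** SAP 6.4 admits to mITT only randomized Part 2 subjects with "at least one dose of study treatment and at least one postbaseline ISNCSCI assessment". The same section states: "Efficacy outcomes for Part 2 will be evaluated using the mITT analysis set". Section 9.3 repeats that "all Part 2 efficacy analysis will be conducted using mITT analysis set". The per-protocol set is no wider: "The Per Protocol Set (PPS) will be a subset of mITT" (SAP 6.7). Protocol 15.6 already had a similar condition for its Full Analysis Set, namely subjects randomized, "treated with at least 1 dose of investigational product, and with at least one post-baseline assessment of efficacy".

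Tables 3, 4 and 5 of the SAP (sections 3.1.2.1.4, 3.1.2.1.6 and 3.1.2.4.6) treat the absence of any post-baseline assessment as an intercurrent event and handle it identically: "Patients who experienced the intercurrent event will be excluded from analysis in line with a principal stratum strategy".

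Two sensitivity analyses bear on dropout. In SAP 8.5.2.1.2 the MNAR analysis has "missing data for all subjects imputed from a regression model estimated from patients in the placebo group", with no analysis set named. In Table 5, a subject who leaves the study before the Day 169 assessment is "considered to be Non-Responder (4='No change"; section 8.5.2.2.1 implements this by repeating the PGIC analysis with such subjects scored as unchanged.

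**The concern.** A subject can receive the first intrathecal dose and leave without being examined again. Under mITT that subject is removed after randomization, for a reason that treatment could influence. The placebo-based imputation and the PGIC composite analysis exist to show whether the conclusions survive informative dropout. If both run on mITT, they inherit the selection of the analysis they are meant to test, and the earliest leavers are the ones missed.

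The estimand label adds to the problem. A principal stratum is defined by what would happen to a subject under both arms, for example those who would be assessed whichever arm they were given. Dropping subjects because no assessment was observed under the arm they received does not identify such a group. The population attribute in SAP 3.1.2.1.2 refers only to the entry criteria and does not mention the restriction.

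**Working it through.** **Tracing one subject.** Take a subject who is randomized, dosed on Day 1 and never examined again.

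1. *mITT (6.4).* Protocol Table 6 schedules the first post-baseline ISNCSCI at Day 21. This subject has none and is out.
2. *Per-protocol set (6.7).* A subset of mITT, so out.
3. *Primary MMRM (8.5.2.1).* Run on mITT, so out.
4. *MNAR imputation (8.5.2.1.2).* The text speaks of all subjects and names no set. The completed datasets are analysed with the 8.5.2.1 model, which is specified on mITT, and 6.4 and 9.3 put all Part 2 efficacy on mITT. Exclusion is the implied reading, though it is not stated outright.
5. *PGIC responder rate (8.5.2.2).* The denominator is mITT, so out.
6. *PGIC composite (Table 5, 8.5.2.2.1).* The subject meets two rows: no post-baseline assessment (exclude) and discontinuation before Day 169 (Non-Responder). The table does not say which governs. The analysis repeats the 8.5.2.2 comparison on its mITT denominator, so exclusion prevails.
7. *Spasticity and pain scores (8.8.7).* Analysed on the Safety Population, but by the same MMRM, which needs a post-baseline value. Not recovered.
8. *All Randomized Set (6.1).* Section 8.2 uses it for disposition. No efficacy analysis is assigned to it.

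Planned efficacy analyses that count this subject, as written: none.

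**Who escapes the gap.** Protocol 9.1 calls for the early-termination evaluation at withdrawal, and the 253/ET column of Protocol Table 6 includes ISNCSCI. Under SAP 7.2 an examination on Days 2 to 42 maps to the Day 21 window. A withdrawing subject who attends therefore enters mITT. The gap covers only those who do not attend, such as subjects lost to follow-up or who withdraw consent for further data collection.

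**Size.** Inputs from Protocol 15.1: difference 5, SD 4, two-sided alpha 0.05, 12 per arm for 80% power, about 16 per arm randomized. The 12 reproduces: a two-sample t-test has 79.6% power at 11 per arm and 83.3% at 12. Neither document gives a dropout rate, so the number of leavers *k* is an assumption, taken as 0 to 2.

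*UEMS.* Suppose *k* of 16 AXER-204 subjects leave unexamined and would have matched placebo, while those retained show a 5-point difference. Counting all dosed subjects:

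5 × (16 − *k*)/16

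- *k* = 0: 5.00
- *k* = 1: 5 × 15/16 = 4.69 (6.25% lower)
- *k* = 2: 5 × 14/16 = 4.38 (12.5% lower)

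The mITT estimate stays at 5.00 throughout. A placebo leaver imputed at the placebo mean would not move the difference. Loss of power is minor: 92.8% at 16 v 16, 90.9% at 14 v 16.

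*PGIC.* The responder counts below are invented to show sensitivity. Placebo is set at 3/16; entries are two-sided Fisher p-values.

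| AXER-204 responders | leaver scored Non-Responder (of 16) | 1 excluded (of 15) | 2 excluded (of 14) |
|---|---|---|---|
| 8 | 0.135 | 0.066 | 0.057 |
| 9 | 0.066 | 0.029 | 0.024 |
| 10 | 0.029 | 0.011 | 0.009 |

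Only the middle row crosses 0.05. One subject can decide the result at this sample size, but need not.

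**The case against.** The affected group is small and may be empty. Subjects who stop treatment are still followed (Protocol 15.4, SAP 7.3.2), and the early-termination visit brings withdrawals who attend it into mITT. That stands, and it caps the size of the point.

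A reader might infer that these subjects disappear from the trial. They do not. They are in the Safety Population (SAP 6.2), and the disposition table (8.2) reports discontinuation reasons and analysis-set membership by arm, so an imbalance would be visible. Safety and pharmacokinetics are the primary objectives of Part 2.

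A reader might also infer that the MNAR imputation cannot reach them. Section 8.5.2.1.2 refers to all subjects and names no set, whereas its third analysis does name the per-protocol set. Exclusion is the better reading given 6.4, 8.5.2.1 and 9.3, but it remains an inference, and two programmers could differ.

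Nor do the documents support assuming four leavers, which would give 5 × 12/16 = 3.75. Protocol 15.1 attributes the increase from 12 to 16 per arm to uncertain historical assumptions as well as missing data. Nothing shows that early exit differs by arm either: placebo subjects undergo the same procedure at the same volume and intervals. The UEMS figures restate an assumption and do not measure bias.

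Finally, the SAP did not invent the post-baseline requirement, and SAP section 10 reports that the Day 169 primary comparison was not significant. There is no positive primary result to overturn. The Table 5 conflict, the unnamed MNAR set and the wrong label remain.

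**Conclusion.** The point holds for efficacy only. Dosed subjects with no post-baseline ISNCSCI are outside every planned Part 2 efficacy analysis. This is firmest for the PGIC composite analysis, where Table 5 gives two incompatible instructions and the denominator settles the matter for exclusion. For the MNAR imputation it is the implied reading of an unstated analysis set. The principal stratum label for this row is incorrect in all three tables.

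The practical effect is limited: no effect if no such subject exists, and about 0.3 to 0.6 UEMS points on an assumed 5-point difference for 1 or 2 leavers, if all are on AXER-204 and would have matched placebo. A PGIC comparison could cross 0.05 on one subject, but only for particular counts. The use of mITT for the primary MMRM is not in dispute. The change is worth making because these two analyses should cover the dropout they were written to test, and because the Day 253 analyses follow the same rules.

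**What to change.** - **Primary analysis:** leave the MMRM on mITT.
- **SAP 8.5.2.1.2:** state that the placebo-based MNAR imputation and its MMRM are run on all randomized and dosed Part 2 subjects, including those with only a baseline value. The MAR imputation can stay as it is, since a baseline-only subject adds almost nothing to the treatment difference under that assumption.
- **SAP Table 5 and 8.5.2.2.1:** run the PGIC composite analysis on the same set and score a subject with no post-baseline assessment as a Non-Responder, so that one row governs.
- **SAP Tables 3 to 5, this row only:** remove the principal stratum wording. In Tables 3 and 4 say plainly that these subjects are not in mITT; in Table 5 say that they are scored as Non-Responders.
- **Timing:** SAP section 10 shows that Day 169 data were already unblinded and analysed, so any Day 169 rerun must be labelled post hoc and supplementary. For Day 253 the change can precede the final lock, but the SAP should record that sponsor staff had by then seen unblinded Day 169 results.

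The cost is SAP wording and a wider input dataset for two analyses already planned. Baseline is assessed before the first dose (Protocol 11.2.2), so no new data are needed. The downside is a slightly less favourable sensitivity estimate if such subjects exist. If none do, nothing changes, and one sentence saying so closes the question.
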